Pertinent page	Before Amendment (Ver. 4, April 24, 2017)			After Amendment (Ver. 5, August 31, 2018)			Reason for Amendment
			
separate sites, 1.0 mL each, among the following sites: right or left upper arm, right or left abdomen, or right or left thigh.
 
(The study drug may be given subcutaneously in 2 separate sites, 2 mL each, only if the investigator or subinvestigator judges that the study drug can be administered properly.)
 
a: When subjects insufficiently respond to the treatment or when their disease relapses, dose escalation from 200 mg to 400 mg will be allowed only once (6 repeated subcutaneous administrations of E6011 400 mg every 2 weeks).
		
subcutaneously in 1 site only if the investigator or subinvestigator judges that the study drug can be administered properly.)
		confirmed
				400 mg ^a	4 mL (4 vials ^c)	
Study drug will be given subcutaneously in 4 separate sites, 1.0 mL each, among the following sites: right or left upper arm, right or left abdomen, or right or left thigh.
 
(The study drug may be given subcutaneously in 2 separate sites, 2 mL each, only if the investigator or subinvestigator judges that the study drug can be administered properly.)
	
						
a: When subjects insufficiently respond to the treatment, repeated subcutaneous administration (400 mg of E6011 every 2 weeks) will be allowed.
	

Pertinent page	Before Amendment (Ver. 4, April 24, 2017)	After Amendment (Ver. 5, August 31, 2018)	Reason for Amendment
P28, 9.4.4 Selection of Doses in the Study	
(text omitted)
 
In the Extension Phase, subjects will receive 200 mg administrations of E6011 (central dose) every 2 weeks. When subjects insufficiently respond to the treatment or when their disease relapses in the Extension Phase (show no improvement from the Observation Phase in both of tender joint counts and swollen joint counts at 2 consecutive assessments), dose escalation will be allowed only once (6 administrations of E6011 400 mg every 2 weeks). As the guidelines indicate that drug therapies for RA should be reviewed every 3 or 6 months, it is appropriate to set the period for administration of E6011 400 mg every 2 weeks to be 3 months (6 administrations).
	
(text omitted)
 
In the Extension Phase, subjects will receive 200 mg administrations of E6011 (central dose) every 2 weeks. However, when subjects insufficiently respond to the treatment (E6011 200 mg every 2 weeks), dose escalation will be allowed (E6011 400 mg every 2 weeks).
	To revise the dose escalation criteria and abolish the restrictions on the number of dose escalations
P43, Table 4 Schedule of Procedures/Assessments in Study E6011-J081-201 70 days after the last dosing: Immunocytes such as blood CX3CR1-positive cells	(no text)	
X^k (Blood collection for immunocytes such as blood CX3CR1-positive cells 70 days after administration was added)
 
k. Will only be conducted if blood sample is judged to be feasible at the visit.
	To evaluate changes in parameters such as CX3CR1-positive cells after administration as an exploratory investigation

Pertinent page	Before Amendment (Ver. 4, April 24, 2017)	After Amendment (Ver. 5, August 31, 2018)	Reason for Amendment
P44, 9.5.2.2 Volume of Blood Samples Table 5	See following pages		To evaluate changes in parameters such as CX3CR1-positive cells after administration as an exploratory investigation To revise the text

(Before Amendment) Table 5 Volume of Blood Samples

Test item	Volume per sampling	Screening Phase	Observation Phase	Treatment Phase	Extension Phase	Follow-up Phase
		Days -42 to -1	Predose of Day 1	Weeks 1 to 24	Weeks 26 to 104	
Viral test, syphilis test, TB test	26 mL	once			twice	
Erythrocyte sedimentation rate	2 mL	once	once	7 times	20 times	
Hematology	2 mL	once	once	7 times	20 times	once
Blood chemistry		once	once	7 times	20 times	once
Pregnancy test	10 mL	(once) ^a		(twice) ^a	(3 times) ^a	
Serum KL-6		(once) ^a		(twice) ^a	(twice) ^a	
Anti-JCV antibody test	3 mL	once		once	3 times	
Blood CD4-positive cells	2 mL	once		twice	3 times	
RF, anti-CCP antibody, MMP-3	4 mL	once	once	7 times	20 times	once
Autoantibody	3 mL		once	twice	3 times	
Serum TRACP-5b concentration			(once) ^a	(twice) ^a	(twice) ^a	
β-D glucan	3 mL	once		twice	twice	
Vasculitis marker tests	5.8 mL		once	twice	6 times	
Serum E6011 concentration	2 mL		once ^b	8 times ^b	20 times ^b	
Serum anti-E6011 antibody	or 5 mL		once ^b	6 times ^b	20 times ^b	
Serum total FKN			(once) ^a			
Serum cytokine concentration, serum LRG1, and Ang2	5 mL		once	3 times	twice	
Vectra TM DA			(once) ^a	(twice) ^a	(twice) ^a	
Immunocytes such as blood CX3CR1-positive cells	5 mL		once	4 times	once	
Each Phase		52.0 mL	41.8 mL	225.6 mL	591.8 mL	16 mL
Screening to Week 24			319.4 mL			
Screening to Week 104			911.2 mL			
Screening to the Follow-up Phase				927.2 mL		

a: Blood collections for these items (inside the brackets) are included in those for the items just above.

b: The volume of blood sample is 5 mL at the time point for assessing both serum E6011 concentration and serum anti-E6011 antibody and 2 mL at the time point for assessing serum E6011 concentration only.

(After Amendment) Table 5 Volume of Blood Samples

Test item	Volume per sampling	Screening Phase	Observation Phase	Treatment Phase	Extension Phase	Follow-up Phase
		Days -42 to -1	Predose of Day 1	Weeks 1 to 24	Weeks 26 to 104	
Viral test, syphilis test, TB test	26 mL	once			twice	
Erythrocyte sedimentation rate	2 mL	once	once	7 times	20 times	
Hematology	2 mL	once	once	7 times	20 times	once
Blood chemistry		once	once	7 times	20 times	once
Pregnancy test	10 mL	(once) ^a		(twice) ^a	(3 times) ^a	
Serum KL-6		(once) ^a		(twice) ^a	(twice) ^a	
Anti-JCV antibody test	3 mL	once		once	3 times	
Blood CD4-positive cells	2 mL	once		twice	3 times	
RF, anti-CCP antibody, MMP-3	4 mL	once	once	7 times	20 times	once
Autoantibody	3 mL		once	twice	3 times	
Serum TRACP-5b concentration			(once) ^a	(twice) ^a	(twice) ^a	
β-D glucan	3 mL	once		twice	twice	
Vasculitis marker tests	5.8 mL		once	twice	6 times	
Serum E6011 concentration	2 mL		once ^b	8 times ^b	20 times ^b	
Serum anti-E6011 antibody	or 5 mL		once ^b	6 times ^b	20 times ^b	
Serum total FKN			(once) ^a			
Serum cytokine concentration, serum LRG1, and Ang2	5 mL		once	3 times	twice	
Vectra TM DA			(once) ^a	(twice) ^a	(twice) ^a	
Immunocytes such as blood CX3CR1-positive cells	5 mL		once	4 times	once ^c	once ^d
Each Phase		52.0 mL	41.8 mL	225.6 mL	591.8 mL	21 mL
Screening to Week 24			319.4 mL			
Screening to Week 104			911.2 mL			
Screening to the Follow-up Phase			932.2 mL			

a: Blood collections for these items (inside the brackets) are included in those for the items just above.

b: The volume of blood sample is 5 mL at the time point for assessing both serum E6011 concentration and serum anti-E6011 antibody and 2 mL at the time point for assessing serum E6011 concentration only.

c: Twice for subjects who discontinue treatment later than Week 52

d: Will only be conducted if blood collection is judged to be feasible at the visit.

Overview of Protocol Amendment between Ver. 5 and Ver. 6

A Dose Response Study of E6011 in Subjects with Rheumatoid Arthritis Inadequately Responding to Methotrexate

(The parts of change: underline)

Protocol body

Pertinent page	Before Amendment (Ver. 5, August 31,2018)	After Amendment (Ver. 6, March 25, 2019)	Reason for Amendment
P7, 2. CLINICAL PROTOCOL SYNOPSIS Concomitant Drug/Therapy P31, 9.4.7.1.2 Restricted Concomitant Drugs	(no text)	
<Restricted Concomitant Drugs>
 
After the date Version 6 of the protocol is approved by IRB, dose reduction, dose interruption, dose increase following the dose reduction (up to the initial dose level), and restarting administration after interruption will be allowed for MTX, folic acid, corticosteroids, or herbal medicine indicated for RA).
 
There will be no restrictions in using NSAIDs (oral, suppository, or topical).
	Because it was considered unnecessary to conduct any non-safety assessments
P8, 2. CLINICAL PROTOCOL SYNOPSIS Assessments	(no text)	
After the date Version 6 of the protocol is approved by IRB, it is unnecessary to conduct assessments other than <safety>.
	Because it was considered unnecessary to conduct any non-safety assessments
P19, 7. INTRODUCTION	(no text)	
The last subject entered the Extension Phase (open-label) in March 2018, and all subjects had completed 52 weeks of treatment with E6011 by March 2019. Consequently, it was considered unnecessary to conduct any non-safety assessments after March 2019, and the protocol will be revised to Version 6.
	Because it was considered unnecessary to conduct any non-safety assessments

Pertinent page	Before Amendment (Ver. 5, August 31,2018)	After Amendment (Ver. 6, March 25, 2019)	Reason for Amendment
P26, 9.3.3 Removal of Subjects From Therapy or Assessment	(no text)	
(9) When the investigator or subinvestigator judges that efficacy of E6011 is insufficient, after the date Version 6 of the protocol was approved by IRB
 
(10) When the investigator or subinvestigator judges that there are other effective treatment options available besides continuing this study, after the date Version 6 of the protocol was approved by IRB
	To add provisions
P30, 9.4.7 Prior and Concomitant Therapy	(no text)	
After the date Version 6 of the protocol is approved by IRB, it is unnecessary to record concomitant medications/therapies in the CRF.
	Because it was considered unnecessary to conduct any non-safety assessments
P33, 9.5.1.3 Efficacy Assesments	(no text)	
After the date Version 6 of the protocol is approved by IRB, it is unnecessary to conduct assessments for efficacy.
	Because it was considered unnecessary to conduct any non-safety assessments
P34, 9.5.1.4 Pharmacokinetic, Pharmacogenomic, Biomarker, and Immunogenicity Assessments	(no text)	
After the date Version 6 of the protocol is approved by IRB, it is unnecessary to conduct assessments for pharmacokinetic, pharmacogenomic, biomarker, and immunogenicity. However, pharmacokinetic and immunogenicity assessments will be conducted at discontinuation.
	Because it was considered unnecessary to conduct any non-safety assessments

Pertinent page	Before Amendment (Ver. 5, August 31,2018)	After Amendment (Ver. 6, March 25, 2019)	Reason for Amendment
P40, 9.5.2.1 Study Schedule	(no text)	After the date Version 6 of the protocol is approved by IRB, it is unnecessary to conduct "tender and swollen joint counts/ESR", "VAS/HAQ", "joint X-rays", "RF/anti-CCP antibody/MMP-3", "serum E6011 concentration", "serum anti-E6011 antibody", "serum total FKN concentration", "cytokines/LRG1/Ang2", "TRACP-5b", "CX3CR1-positive cell count", or "VectraTM DA". However, assessments of "serum E6011 concentration" and "serum anti-E6011 antibody" will be conducted at discontinuation.	Because it was considered unnecessary to conduct any non-safety assessments
P44, 9.5.2.1 Study Schedule Table 4 Remarks	(no text)	1 After the date Version 6 of the protocol is approved by IRB, applicable assessments will not be conducted. However, assessments of serum E6011 concentration and serum anti-E6011 antibody will be conducted at discontinuation.	Because it was considered unnecessary to conduct any non-safety assessments
P45, 9.5.2.2 Volume of Blood Samples	(no text)	As it is unnecessary to conduct non-safety assessments after the date Version 6 of the protocol is approved by IRB, the volume of blood samples may be lower in applicable subjects.	Because it was considered unnecessary to conduct any non-safety assessments

Page(s) removed - non-English text removed

2 LIST OF ABBREVIATIONS AND DEFINITIONS OF TERMS

Abbreviation	Term
ACR	American College of Rheumatology
AE	adverse event
ATC	anatomical therapeutic class
ANCOVA	analysis of covariance
Ang2	angiopoietin 2
ATC	anatomical therapeutic class
BLQ	below the limit of quantification
BMI	body mass index
BP	Blood pressure
CCP	cyclic citrullinated peptide
CDAI	clinical disease activity index
CI	confidence interval
CRF	case report form
CRP	C-reactive Protein
CSR	clinical study report
CTCAE	Common Terminology Criteria for Adverse Events
DAS28	disease activity score in 28 joints,
DP	Decimal places
EGF	epidermal growth factor
ESR	Erythrocyte Sedimentation Rate
EULAR	European League Against Rheumatism
FAS	full analysis set
γ-GTP	γ-glutamine transpeptidase
HAQ	Health Assessment Questionnaire
HAQ-DI	Health Assessment Questionnaire Disability Index
IL	Interleukin
LLOQ	lower limit of quantification
LOCF	last observation carried forward

Abbreviation	Term
LRG1	leucine-rich alpha-2 glycoprotein 1
MedDRA	Medical Dictionary for Regulatory Activities
MMP	matrix metalloproteinase
mTSS	modified total sharp score
MTX	Methotrexate
NCI	National Cancer Institute
NRI	non-responder imputation
OC	observed cases
PD	pharmacodynamics
PK	Pharmacokinetic
PPS	per protocol set
PT	preferred term
RA	rheumatoid arthritis
RF	rheumatoid factor
SAE	serious adverse event
SAP	statistical analysis plan
SD	standard deviation
SDAI	simple disease activity index
SI	Système International
SJC	swollen joint counts
SJC28	swollen joint counts in 28 joints
SJC66	swollen joint counts in 66 joints
SOC	system organ class
TEAE	treatment-emergent adverse event
TEMAV	treatment-emergent markedly abnormal laboratory value
TJC	tender joint counts
TJC28	tender joint counts in 68 joints
TJC68	tender joint counts in 28 joints
TLG	tables, listings, and graphs
TNF-RI	tumor necrosis factor receptor-I

Abbreviation	Term
TRACP-5b	tartrate resistant acid phosphatase 5b
VAS	visual analog scale
VCAM-1	vascular cell adhesion molecule-1
VEGF	vascular endothelial growth factor
WHO DD	World Health Organization Drug Dictionary

3 INTRODUCTION

The purpose of this statistical analysis plan (SAP) is to describe the procedures and the statistical methods that will be used to analyze and report results for Eisai Protocol E6011-J081-201. Since the Version 6 of the protocol defined that it was unnecessary to conduct assessments other than safety assessment, all the efficacy analysis will be conducted until Week 84, that is the latest Visit of ongoing subjects at the time of amendment of the protocol.

Statistical methods of Extension Phase are provided in this document.

3.1 Study Objectives

3.1.1 Primary Objectives

- To evaluate the efficacy of E6011 compared with placebo by ACR20 response rate at Week 12 as a primary endpoint
- To evaluate the safety and tolerability of E6011

3.1.2 Secondary Objectives

- To evaluate the effect of E6011 on suppressing radiographic progression of joint destruction at Week 24
- To evaluate the pharmacokinetics (PK) and immunogenicity of E6011

3.1.3 Exploratory Objective

- To explore the PK/pharmacodynamics (PD) and biomarkers of E6011

3.2 Overall Study Design and Plan

This study is a multicenter, randomized, double-blind, placebo-controlled, parallel-group comparison study. The following 4 treatment groups are selected for the study: E6011 100 mg, 200 mg, 400 mg, and placebo. In the E6011 100 mg, 200 mg, and placebo groups, subjects will receive 100 mg, 200 mg, or placebo at Weeks 0, 1, 2, and every 2 weeks subsequently. In the E6011 400 mg group, subjects will receive 400 mg at Weeks 0, 1, 2, 4, 6, 8, 10 and then 200 mg every 2 weeks subsequently.

The study consists of Screening, Observation, Treatment, Extension, and Follow-up Phases.

Undergoing screening assessments within 42 days prior to the study treatment, subjects with the certain eligibility confirmed in the Observation Phase will be allocated into any of the 100 mg, 200 mg, 400 mg, or placebo groups at a 1:2:2:2 ratio through dynamic allocation using the following factors: C- reactive protein (CRP) level at Screening, Rheumatoid Arthritis (RA) Duration, and Prior Use of Biologics Treatment.

In the Treatment Phase (24 weeks), subjects will receive either E6011 or placebo at Weeks 0, 1, 2, and every 2 weeks until Week 22 in a double-blind manner.

Subjects who complete evaluations at Week 24 of the Treatment Phase will enter the Extension Phase. The Extension Phase is up to Week 104 from the starting of the study treatment, and subjects will receive an open-label E6011 200 mg every 2 weeks until Week 102. When subjects insufficiently respond to the treatment or when their disease relapses in the Extension Phase (show no improvement from Observation Phase in both of tender joint counts (TJC) and swollen joint counts (SJC) at 2 consecutive assessments with an interval of ≥ 1 week), a dose escalation will be allowed.

Follow-up investigations will be conducted on-site 28 days after the completion of the study or the discontinuation of the treatment, and either an on-site or telephone-interview investigation will be conducted 70 days after the last dosing.

4 DETERMINATION OF SAMPLE SIZE

The sample size was based on an expected ACR20 response rate of 30% at Week 12 in the placebo group and at least 60% in both of the E6011 200 mg and 400 mg groups, as per previous Study 103 and the results from other drugs for treatment of RA. Although multiplicity adjustment using Hochberg method will be carried out in the primary analysis, sample size was calculated at a 1-sided significance level of $\alpha=0.0125$ ($\alpha=0.025/2$) conservatively. The sample sizes of 50 for E6011 200 mg, 400 mg, and placebo will have 91% power to detect a difference in response rate of 35% between placebo and each E6011 group and will have 79% power to detect a difference in response rate of 30% based on a chi-square test.

5 STATISTICAL METHODS

All descriptive statistics for continuous variables will be reported using mean, standard deviation (SD), median, minimum and maximum. Categorical variables will be summarized as number (percentage) of subjects.

5.1 Study Endpoints

5.1.1 Primary Endpoint

- ACR20 response rate at Week 12

The ACR20 response is defined as if the following 3 criteria (ACR components) are met:

1. Greater than or equal to 20% reduction from baseline in the TJC in 68 joints (TJC68)
2. Greater than or equal to 20% reduction from baseline in the SJC in 66 joints (SJC66)
3. Greater than or equal to 20% reduction from baseline in at least 3 of the following 5 assessments:
 - Physician's Global Assessment of Disease Activity (VAS)
 - Patient's Global Assessment of Disease Activity (VAS)
 - Patient's Assessment of Pain (VAS)
 - HAQ-DI
 - CRP

5.1.2 Secondary Endpoints

- ACR20, ACR50, and ACR70 response rate at each visit (excluding ACR20 at Week 12)
- Values and change from baseline in ACR components (TJC, SJC, VAS [patient's assessment of pain, patient's global assessment of disease activity and physician's global assessment of disease activity], functional assessment by subjects [HAQ-DI], and CRP·ESR), DAS28-ESR, DAS28-CRP, SDAI, and CDAI at each visit
- EULAR response criteria at each visit; subjects will be classified based on DAS28-ESR or DAS28-CRP
- DAS28-ESR, DAS28-CRP, SDAI, CDAI, and Boolean remission rates at each visit
- Values and change from baseline in modified total sharp score (mTSS) at each visit

The ACR50 response is defined similar to the ACR20 with a 50% reduction.

The ACR70 response is defined similar to the ACR20 with a 70% reduction.

The DAS28-CRP calculates on the following formula, and disease activity is categorized as High at > 4.1 , Moderate at > 2.7 and ≤ 4.1 , Low at ≤ 2.7 , and Remission at ≤ 2.3 .

$$0.56 \times \text{sqrt}\{\text{TJC in 28 joints (TJC28)}\} + 0.28 \times \text{sqrt}\{\text{SJC in 28 joints (SJC28)}\} + 0.36 \times \ln\{\text{CRP (mg/dL)} \times 10 + 1\} + 0.014 \times \text{Patient's Global Assessment of Disease Activity (VAS) (mm)} + 0.96$$

The DAS28-ESR will be calculated on the following formula, and disease activity is categorized as High at > 5.1 , Moderate at > 3.2 and ≤ 5.1 , Low at ≤ 3.2 , and Remission at < 2.6 .

$$0.56 \times \text{sqrt}\{\text{TJC28}\} + 0.28 \times \text{sqrt}\{\text{SJC28}\} + 0.70 \times \ln\{\text{ESR (mm/h)}\} + 0.014 \times \text{Patient's Global Assessment of Disease Activity (VAS) (mm)}$$

EULAR Response Criteria:

Present DAS28	DAS28 change from baseline		
	<-1.2	≥ -1.2 and <-0.6	≥ -0.6 (missing included)
Low	Good response	Moderate response	No response
Moderate	Moderate response	Moderate response	No response
High	Moderate response	No response	No response

The CDAI will be calculated on the following formula, and disease activity is categorized as High at > 22 , Moderate at > 10 and ≤ 22 , Low at ≤ 10 , and Remission at ≤ 2.8 .

$$\begin{aligned} & \text{SJC28} + \text{TJC28} \\ & + \text{Patient's Global Assessment of Disease Activity (VAS) (mm)/10} \\ & + \text{Physician's Global Assessment of Disease Activity (VAS) (mm)/10} \end{aligned}$$

The SDAI will be calculated on the following formula, and disease activity is categorized as High at > 26 , Moderate at > 11 and ≤ 26 , Low at ≤ 11 , and Remission at ≤ 3.3 .

$$\begin{aligned} & \text{SJC28} + \text{TJC28} \\ & + \text{Patient's Global Assessment of Disease Activity (VAS) (mm)/10} \\ & + \text{Physician's Global Assessment of Disease Activity (VAS) (mm)/10} + \text{CRP (mg/dL)} \end{aligned}$$

The Boolean remission is defined as satisfied all of the following conditions:

1. $\text{TJC68} \leq 1$
2. $\text{SJC66} \leq 1$
3. $\text{CRP (mg/dL)} \leq 1$
4. Disease activity assessments VAS (mm) by subjects ≤ 10

5.2 Study Subjects

5.2.1 Definitions of Analysis Sets

Definition of analysis sets are as follows:

- The Full Analysis Set (FAS) is the group of randomized subjects who received at least 1 dose of study drug after 24 weeks to 104 weeks and had at least 1 postdose efficacy measurement after 24 weeks to 104 weeks
- The Safety Analysis Set is the group of subjects who received at least 1 dose of study drug after 24 weeks to 104 weeks and had at least 1 postdose safety assessment after 24 weeks to 104 weeks

The number of subjects randomized, the number and the percentage of subjects included in each analysis set, and the number and the percentage of subjects excluded from each analysis set will be presented by treatment group and overall.

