9.7 Statistical Methods

Statistical analyses will be performed by using SAS or other validated statistical software as needed after unblinding. In this study, the statistical analysis in the Treatment Phase will be performed after the database in the Treatment Phase is locked and the data is unblinded, and then final analysis will be performed by using all data after the database throughout the study period is locked. The details will be described separately in the Statistical Analysis Plan (SAP). SAP for the Treatment Phase and the entire study (the Treatment and Extension Phases) will be finalized before each database lock.

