9.7.1.2 Definitions of Analysis Sets

The Full Analysis Set (FAS) is the group of randomized subjects who received the study drug and had at least 1 evaluable postdose primary efficacy measurement.

The Per Protocol Analysis Set (PPS) is the group of subjects who sufficiently complied with the protocol. Details of the PPS criteria will be determined before database lock and unblinding and will be specified in the Statistical Analysis Plan.

The Safety Analysis Set is the group of subjects who received the study drug and had at least 1 evaluable postdose safety assessment.

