5.3.5 Handling of Missing Data, Dropouts, and Outliers

For the efficacy analyses, approaches to handling missing data for continuous variables, except mTSS, will be the observed cases (OC) method and the last observation carried forward (LOCF) method; binary variables and EULAR response criteria will be the observed cases (OC) method, the last observation carried forward (LOCF) method and the non-responder imputation (NRI) method as each visit.

mTSS value at Week 24, Week 52 and Week 76 will be extrapolated from values of baseline and values of postbaseline, which will be used in summary statistics. The linear extrapolation method will be used for analysis of the structural progression endpoint (van der Heijde mTSS) to impute missing data at time points when analyses are conducted (including the analyses at Week 24, Week 52 and Week 76). For patients who discontinue the study or the study treatment or for patients who miss a radiograph for any reason, baseline data and the most recent radiographic data prior to discontinuation or the missed radiograph, adjusted for time, will be used for linear extrapolation to impute missing data at subsequent time points. All patients originally randomized to placebo will be switched to active treatment at Week 24; Missing postbaseline values will be imputed only if both a baseline value and a postbaseline value from another time point are available, as long as the patient was on the same treatment at each applicable time point.

Calculation for value of mTSS extrapolation will be derived by follow formula:

- Week 24 = (Postbaseline) + (Postbaseline – Baseline) * ((24 – (Study Day of Postbaseline / 7) / Study Day of Postbaseline / 7)
- Week 52 = (Postbaseline) + (Postbaseline – Baseline) * ((52 – (Study Day of Postbaseline / 7) / Study Day of Postbaseline / 7)
- Week 76 = (Postbaseline) + (Postbaseline – Baseline) * ((76 – (Study Day of Postbaseline / 7) / Study Day of Postbaseline / 7)

The two individual components of mTSS (Erosion and joint space narrowing [JSN] score) will be analyzed in the same way as the mTSS.

For the safety analyses for continuous value, descriptive statistics are used OC method and LOCF method, this is applied only the last observation of each phase, in tables and figures.

In the cases of laboratory result contains less (or more) than quantitation limit value is treated as:

- a. zero, when less than quantitation limit value,

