5.6 Safety Analyses

All safety analyses will be performed on the Safety Analysis Set. Safety data, presented by treatment group, will be summarized on an “as treated” basis using descriptive statistics (eg, n, mean, SD, median, minimum, maximum for continuous variables; n [%] for categorical variables). Safety variables include treatment-emergent adverse events (TEAEs), clinical laboratory parameters, vital signs, 12-lead ECG results, chest x-ray, neurological findings, and blood CD4 positive cell count. Day 1 for all safety analyses will be defined as the date of the first dose of study drug.

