5.6.1 Extent of Exposure

The extent of exposure to study drug will be characterized by duration of exposure, number of injection dose and study medication compliance for each treatment group. Definition of analysis items are as follows:

- Duration of exposure (weeks) = (Date of Last Dose - Date of First Dose + 14) / 7
- Number of Injection = Count of records with non-zero treatment
- Study Medication Compliance (%) = Number of Injection / Number of Expected Injection * 100

Subject data listings will be provided.

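### The extension SAP limits its analysis sets to subjects dosed after Week 24 but keeps first-dose and Week 0 origins, so its cumulative safety tables and NRI rates leave out everyone who stopped earlier

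*SAP*

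**What the plan says.** **Who is analysed.** SAP 5.2.1 defines the safety set thus: "The Safety Analysis Set is the group of subjects who received at least 1 dose of study drug after 24 weeks to 104 weeks", with a safety assessment in the same period. The FAS is "randomized subjects who received at least 1 dose of study drug after 24 weeks to 104 weeks", with an efficacy measurement in that period. Only subjects who complete the Week 24 evaluations enter the Extension Phase (Protocol 9.1.4; SAP 3.2), so anyone who stopped earlier is outside both sets. The same SAP section adds that "the number and the percentage of subjects excluded from each analysis set will be presented by treatment group and overall".

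**Where counting starts.**
- SAP 5.6: "Day 1 for all safety analyses will be defined as the date of the first dose of study drug".
- SAP 5.6.1: "Duration of exposure (weeks) = (Date of Last Dose - Date of First Dose + 14) / 7".
- SAP 5.6.2 judges treatment-emergent adverse events (TEAEs) against the pretreatment state. It ends the window 70 days after the last dose and gives no start at the extension.
- SAP 8.1.1 takes baseline as the last value before first dosing.
- SAP 5.3.5 handles binary endpoints by observed cases, LOCF and "the non-responder imputation (NRI) method as each visit". SAP 5.4 runs efficacy on the FAS above.

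**What the protocol planned.** Protocol 9.7.1.2 has no Week 24 condition: "The Safety Analysis Set is the group of subjects who received the study drug and had at least 1 evaluable postdose safety assessment". Protocol 9.7 calls for one SAP for the Treatment Phase and one for the entire study, and says that the "final analysis will be performed by using all data after the database throughout the study period is locked". SAP Section 7 lists two changes from the protocol: efficacy only to Week 84, and PK as listings only. The narrower sets are not among them.

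**The concern.** An extension-entrant set is a normal choice for a table of what happened during the extension. The difficulty is pairing it with a clock that starts at Week 0. Weeks 0 to 24 then enter the tables only through people who, by the definition of the set, were still on treatment at the end of them. The table of TEAEs leading to withdrawal, shown by arm and for E6011 overall, cannot contain a withdrawal from the first 24 weeks. A subject who stopped at Week 10 is neither a nonresponder nor in the denominator of the Week 52 NRI rate.

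Safety and tolerability is a primary objective. The restricted sets keep the protocol's names, so a reader of the final tables would naturally take them to cover all treated subjects. If early stopping differs by arm, the side-by-side figures also differ in how strongly each arm has been selected.

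**Working it through.** The plan gives no figure for stopping before Week 24, so there is nothing of its own to reproduce on this point. The check sets the rules side by side and then derives the direction of the effect. Sizes below are illustrations under stated assumptions.

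**1. Set against clock**

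| Item | Who is included | Counted from |
|---|---|---|
| Exposure (SAP 5.6.1) | dosed after Week 24 | first dose |
| TEAEs (SAP 5.6.2) | dosed after Week 24 | no start stated; judged against pretreatment, Day 1 = first dose |
| NRI response (SAP 5.3.5, 5.4, 8.1.1) | dosed after Week 24 | Week 0 baseline |

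**2. NRI response.** Let N be the protocol FAS in an arm, R the responders at a visit after Week 24, and d the share of N that stops before Week 24 and so falls outside the SAP FAS. Under NRI none of the early stoppers is a responder, so R is the same in both sets.

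- Protocol FAS: q = R / N
- SAP FAS: R / [N(1 - d)] = q / (1 - d)

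For any d above 0 the rate goes up. For illustration, q is set to the Week 12 planning rates in SAP Section 4 (30% and 60%), with an arm of 50 and d assumed:

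| d | kept of 50 | 60% becomes | 30% becomes |
|---|---|---|---|
| 5% | 47.5 | 0.60/0.95 = 63.2% | 0.30/0.95 = 31.6% |
| 10% | 45 | 0.60/0.90 = 66.7% | 0.30/0.90 = 33.3% |
| 20% | 40 | 0.60/0.80 = 75.0% | 0.30/0.80 = 37.5% |
| 30% | 35 | 0.60/0.70 = 85.7% | 0.30/0.70 = 42.9% |

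A 30-point gap between arms can move either way:
- 10% lost in both arms: 66.7 - 33.3 = 33.3 points (from unrounded rates).
- Placebo loses 10%, active 20%: 75.0 - 33.3 = 41.7 points.
- Placebo loses 20%, active 10%: 66.7 - 37.5 = 29.2 points.

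**3. Withdrawal due to adverse events.** Let s subjects stop before Week 24, e of them for an adverse event, and let l stop later for an adverse event.

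- All dosed: (e + l) / N
- SAP set: l / (N - s)

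With assumed counts N = 50, s = 5, e = 3, l = 2, the rates are 5/50 = 10.0% and 2/45 = 4.4%. If instead every early stop is for an adverse event and l = 3:
- s = e = 2: 5/50 = 10% against 3/48 = 6.3%.
- s = e = 5: 8/50 = 16% against 3/45 = 6.7%.
- s = e = 8: 11/50 = 22% against 3/42 = 7.1%.

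As early withdrawals rise, the all-dosed figure climbs steeply and the SAP figure hardly moves.

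**The case against.** The strongest reply is that this SAP states in its Introduction that it covers the Extension Phase. Protocol 9.7.1 says that the sections up to 9.7.1.8, including the set definitions, mainly describe the Treatment Phase. Section 9.7.1.9 asks only for similar extension analyses and names no set. On that reading an extension-entrant set is unremarkable. This stands for extension-only tables. It does not explain why the origins stay at first dose, or why Section 7 is silent when Protocol 9.7 promised a SAP for the entire study.

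Second, the start of adverse event counting is my inference. SAP 5.6.2 states only the end, Day 1 could be mere day numbering, and 5.6.1 does not define the first-dose date further. Some wording suggests phase-specific tables: safety LOCF is taken at the last observation of each phase (5.3.5), and biomarkers are summarised for the Extension Phase (5.5.2.2). Table shells are in a separate document. If counting was meant to begin at the Week 24 dose, set and period agree, but the SAP needs to say so.

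Third, a reader might infer that early stoppers vanish from the trial's results. The documents do not support that. Protocol 9.7 plans a separate Treatment Phase analysis in which they stay in the safety set, and Protocol 9.7.1.6.1 counts missing Week 12 outcomes as nonresponse. SAP 5.2.1 reports exclusions by arm, and the disposition summary in 5.2.2 names no restricted set.

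Fourth, extension efficacy is descriptive: there is no primary analysis, covariate or multiplicity adjustment (SAP 5.3.2, 5.3.3, 5.4.1), and all arms are on open-label E6011. This limits the harm to any formal arm comparison. Last, NRI in all dosed subjects would count former-placebo subjects who stopped before Week 24 as nonresponders although they never received E6011. That is why both versions should be shown.

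**Conclusion.** The mismatch is real as the SAP is written. Both sets require a dose and an assessment after Week 24, while exposure, Day 1, the TEAE definition and baseline look back to the start of treatment. The extension SAP's cumulative tolerability figures therefore describe Weeks 0 to 24 in survivors of that period only, and its NRI rates exclude earlier stoppers.

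The direction for NRI is certain for any d above 0: the rate is multiplied by 1/(1 - d). Adverse event withdrawals before Week 24 are all lost from the withdrawal table. The size cannot be computed, because the documents give no early dropout rate; every percentage above rests on assumed values. The TEAE part also assumes that counting starts at first dose, which the text implies but does not state.

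The loss is from this SAP's cumulative tables, not from the trial, and the Week 12 primary result is untouched. The Treatment Phase SAP was not among the documents and could not be checked.

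**What to change.** 1. In SAP 5.2.1, rename the present sets Extension Safety Set and Extension FAS. For tables that use them, start adverse event and exposure counting at the first extension dose (Week 24), and state this in 5.6, 5.6.1 and 5.6.2.
2. For any table counting from first dose (cumulative TEAEs, TEAEs leading to withdrawal, exposure), use the protocol's Safety Analysis Set of dosed subjects, with no Week 24 condition.
3. Show NRI response at each visit to Week 84 in the protocol FAS beside the Extension FAS, with a note that former-placebo subjects who stopped before Week 24 never received E6011.
4. List the change in SAP Section 7.

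The cost is SAP wording and an extra run of existing tables; the data are already collected. The downside is somewhat less favourable withdrawal and response figures, and two NRI columns to explain.
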